**Table 3. Summary of patient participation**

Procedure	Screen	MRI Brain 1	Enrolment	Course 1	Rituximab 1	6 Month Rev	Rituximab 2	MRI Brain 2	12 Month Rev	Course 2	Rituximab 3	18 Month Rev	Rituximab 4	MRI Brain 3	24 Month Rev	30 Month Rev	MRI Brain 4	36 Month Rev	Time (Hrs)	Total Time (Hrs)
Time (wks)	-4	-1	-1	0	10	26	30	48	50	52	62	78	82	100	104	130	152	154		
Screening Visit	1																		1	1
Clinical Rev			1			1			1			1			1	1		1	0.5	3.5
EDSS	1		1			1			1			1			1	1		1	0.5	4
MRI		1						1						1			1		1	4
Screen bloods	1																		0.25	0.25
Rituximab					1		1				1		1						4	16
Total participant hours																			28.8	

**Figure 1. RAMBLE Trial Design**

Following screening participants will be randomized 2:1 to receive either rituximab or placebo at weeks 10 and 30 after each dose of alemtuzumab. Follow up will be for a minimum of 2 years and a maximum of 4 years. Alemtuzumab administered at Week 1 and Week 53 (yellow arrows). Rituximab/placebo administered at Weeks 10 and 30 in each of Years 1 and 2 (blue arrows). Clinic reviews at -4 and -1 weeks and then every 6 months (black arrows). MRI every year (red arrows).

---

## **i. Outcome Measures**

- *Primary outcome measure: the frequency of autoimmune adverse events (autoimmune thyroid disease, idiopathic thrombocytopenia, anti-GBM renal disease and any other autoimmune diseases).*
- *Secondary outcome measures:*
  - *Other adverse events, in particular infections*
  - *Measures of alemtuzumab treatment efficacy*
    - *Time to first relapse or new disease activity on MRI*
    - *Time to first relapse*
    - *Annualised relapse rate*
    - *EDSS*
    - *MSIS-29*
    - *Sustained disability progression*
    - *Number of new T2 lesions on MRI*
    - *Number of new Gd-enhancing lesions on MRI*
  - *Measure of lymphocyte reconstitution*
    - *Total lymphocyte count*
    - *CD4, CD8, CD20 counts*
    - *B-cell subpopulation counts.*

## **j. Data Collection**

- *Data will be collected in an eCRF created using a specifically created REDCap database. This database will be held on Servers maintained by Griffith University and access to the database online will be restricted to study personal at the various sites. Access to the data will be further restricted according to utilisation requirements and for maintaining blinding.*

## **k. Data Storage and Confidentiality**

- *Participants' privacy and confidentiality will be protected through the following:*
  - *Participant information and consent forms will be held in dedicated files for each participant at participating sites. These files will be held in a secure location (locked room, which only clinical staff will have access to).*
  - *Patient specific data will be stored within medical case note files within medical records departments or in electronic medical record systems at each site. Medical records departments at state health facilities have restricted access that only permits those with requisite authority to have access to the files. Queensland Health uses a statewide integrated electronic medical record system (ieMR, IBM Inc) which is password protected.*

- 
- *This is a clinical trial and for safety reasons (accurate identification of participants) it will be essential that all clinically related records are identifiable. However, all centrally recorded patient information (e.g. eCRF) and correspondence with CRO and regulatory bodies will be de-identified. All such records will use a unique participant identification code. Data connecting participant identifying information (participant folders and medical records) will also carry this code ensuring that all participants are potentially re-identifiable at the individual site. These identifiers will not be removed at each site at any point in case of the urgent need to re-identify a participant for safety reasons (e.g. unblinding of treatment allocation). All safety and statistical analyses will be conducted on fully de-identified data.*
  - *In accordance with International publication and regulatory requirements fully de-identified aggregate data and where necessary raw data will be made available for independent verification of results and regulatory processes. These data will be held on servers at Griffith University in password protected files and only released to third parties if required for regulatory purposes or if requested from other researchers after approval by local human research ethics committee (HREC).*
  - *Under medical practice guidelines and laws participants will have access to their own clinical data as held in the medical records at each participating site.*
  - *All records will be kept for a minimum of 15 years. Paper and electronic documents will be held at each site as part of existing medical record protocols. Trial related documents (participant folders) will be stored locally using secure storage facilities. All central electronic data will be stored on Griffith University servers in password protected files.*
  - *There are no plans for secondary use of data or information (e.g. data banking/sharing).*

## **I. Data Analysis and Statistical Considerations**

- *The primary outcome measure for this study will be frequency of autoimmune adverse events. Because the duration of follow up will not be uniform for all participants and in order to make the maximal use of data the frequency of autoimmune adverse events will be modelled using a Cox Proportional Hazards time to event analysis (with onset of autoimmune adverse event as the event of interest). Although randomisation will be stratified for clinical site and sex, these factors as well as age and disease severity (MSSS) will be included in the model. Analysis will be performed on an intention-to-treat basis.*
- *Secondary outcome measures will be analysed as follows:*
  - *Other adverse events (MedDRA terms) will be compared using frequencies and chi-squared statistics.*

- 
- *Efficacy in terms of MS outcomes will be analysed using time to event analysis (Cox Proportional Hazards method) for annualized relapse rate and sustained disability progression (6 months), including the factors listed above for the primary outcome analysis in the model.*
  - *Other secondary outcomes (e.g. change in EDSS, new T2 and Gd-enhancing MR imaging lesions) at 1 and 2 years will be assessed using linear regression analysis provided assumptions are met (in which case non-parametric methods will be used).*
  - *Any effect of laboratory measures (lymphocyte subsets,) and baseline characteristics will be explored using regression analysis.*
  - *All statistical analyses will be conducted using STATA® v16 software (StatCorp®, US). The primary outcome of this trial will be met if the hazard ratio of autoimmune adverse events in the treatment (rituximab) arm is significantly lower than that seen in the placebo arm. The study is unlikely to have sufficient power to identify any significant differences in the frequency of other adverse events or MS disease outcome measures, but these will be looked at carefully to ensure that these outcomes are similar in the two groups.*

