Alemtuzumab is a monoclonal antibody against CD52 which is a cell surface marker of lymphocytes of unknown function. The antibody is lytic to lymphocytes and causes a profound temporary lymphopenia following intravenous administration. Bone marrow derived lymphocytes begin to re-emerge almost immediately and by 3 months are up to 70% of pre-treatment levels. One of the features of this lymphocyte repopulation is that B-cells re-emerge faster than T-cells. It has therefore been postulated that the extra-thymic self-tolerisation of B-cells in the absence of regulatory T-cells might explain the frequent emergence of autoimmune disease following treatment with alemtuzumab. It has further been suggested that one strategy to ameliorate the emergence of autoimmunity following alemtuzumab, B-cell depleting agents could be used to quell their early re-emergence. B-cell depleting agents have been used to successfully treat autoimmune disease following alemtuzumab.

A recent phase I, open label, single arm clinical trial of rituximab therapy administered whenever B-cell counts reached 50% of baseline levels following treatment of MS with alemtuzumab demonstrated that this approach is safe and potentially completely effective in mitigating the risk of autoimmunity (Class V evidence).

In view of this preliminary data, it is proposed that a phase II, placebo-controlled clinical trial be undertaken with the aim of assessing the effectiveness of B-cell depletion in mitigating the risk of autoimmune disease following treatment with alemtuzumab in pwMS.

---

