## 2. Study Objectives

### a. Research Question and Aims/objectives

- *Primary Objective*
  - *To demonstrate a reduction or complete abrogation of the occurrence of autoimmune disease with administration of rituximab following treatment with alemtuzumab for MS.*
- *Secondary Objectives*
  - *To assess the safety and efficacy (MS disease activity related) of this therapeutic approach.*
  - *To assess the profile of the immune repertoire of T and B-cells that re-emerge with this therapeutic approach.*
  -

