#### **d. Recruitment/ Selection**

- *Potential participants will be recruited through the MS or CNS inflammatory disease clinics of the six participating hospitals with a cap of 20 participants at any single centre. Participants will not be financially compensated for their involvement in this trial but will be reimbursed for any reasonable costs of participation (e.g. parking costs).*
- *Participants will be recruited by neurologists at each site, who having identified a patient who is about to commence treatment with alemtuzumab, will invite the pwMS to participate in the trial. Potential participants will be provided with an introduction and overview of the study by their treating neurologist. Those who are interested in participating will be provided with the Patient Information and Consent Form (PICF) to take away and read and a further visit with one of the study investigators will be arranged at a later date.*
- *Participants will be enrolled in the study at the baseline/screening visit provided they:*
  - 1. *Have given written informed consent*
  - 2. *Meet all the inclusion criteria*
  - 3. *Meet none of the exclusion criteria*
- *Randomisation: Participants will be randomised at enrolment to treatment with rituximab or placebo at a 2:1 ratio. Randomisation will be performed using the randomisation module of the REDCap database based on a random number sequence produced in Excel®, Microsoft (Seattle, CA, USA) stratified by site, sex and age. This randomization sheet will be generated by Assoc/[name]. There will a cap of 20 participants for any single site.*
- *Blinding and allocation concealment: This will be a double-blinded study with both patient and treating physician blinded as to whether the participant is receiving active treatment or placebo. At the screening visit, participants will be assigned a unique participant Screening Number. At the baseline/enrolment visit, after eligibility is confirmed and the full consent form has been signed, a Participant Identification Number (PIDN) will be assigned. PIDNs will be randomly assigned to intervention or placebo groups according to the randomisation code provided by the randomisation sheet. Randomisation*

---

codes will only be visible through REDCap to site pharmacists who will make up the active treatment and placebo. Both rituximab and 0.9% sodium chloride (placebo) are colourless fluids, so will be indistinguishable to treating physician, participants and other staff.

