#### Statistical power calculation

- *A previously published sample size calculation based on a Phase I study suggests that a trial of 80 participants (40 in each arm) would have 80% power with  $p < 0.05$  to detect a reduction in autoimmune adverse events from 40% down to 10%.*
- *Primary analysis will be based on observed data only but a sensitivity analysis where missing data is imputed using maximum likelihood imputation methods will be undertaken.*
- *All statistical analyses will be conducted by our in-house statisticians, [name] and A/[name].*

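### The primary Cox model carries about nine parameters on about 16 expected events, and the success rule names no test although the usual Wald test fails if rituximab has no events

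*Protocol*

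**What the plan says.** The Data Analysis and Statistical Considerations section of the protocol models autoimmune adverse events by Cox regression, by intention to treat. It describes randomisation as stratified by clinical site and sex, and adds that "these factors as well as age and disease severity (MSSS) will be included in the model". The primary outcome "will be met if the hazard ratio of autoimmune adverse events in the treatment (rituximab) arm is significantly lower" than in the placebo arm. The protocol names no test statistic and says nothing about an arm without events.

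The primary objective is "To demonstrate a reduction or complete abrogation of the occurrence of autoimmune disease". The Background says of the phase I study that "this approach is safe and potentially completely effective in mitigating the risk of autoimmunity".

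Under Recruitment/Selection, "Participants will be randomised at enrolment to treatment with rituximab or placebo at a 2:1 ratio", and the randomisation is "stratified by site, sex and age". The power calculation states that "a trial of 80 participants (40 in each arm) would have 80% power" for a fall from 40% to 10%. The protocol gives no expected number of events.

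**The concern.** Two features of the primary analysis matter together.

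- **Too many covariates for the events.** A Cox model with fewer than two events per parameter tends to exaggerate the treatment effect, and its tests can reject too often. The covariate list is in the protocol itself, so a separate analysis plan could not shorten it without departing from the protocol.
- **No test named.** If no rituximab participant has an event, the partial likelihood has no finite maximum: the hazard ratio estimate goes to 0 and its standard error grows without limit. The Wald p-value and confidence interval, which are the usual output for a single Cox coefficient, then carry no information. The objective counts that result as a success.

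At stake are the accuracy of the reported effect and whether the primary conclusion can be defended. If the test were chosen only after an arm turned out to have no events, the choice would be open to challenge.

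**Working it through.** **Inputs from the protocol.** N = 80; allocation 2:1, so about 53 rituximab and 27 placebo; event risks 10% and 40%; six sites; covariates site, sex, age and MSSS.

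**Assumptions.** Site enters as five indicators; age and MSSS are linear; there is no dropout; 40% and 10% are cumulative risks with constant hazards; tests are two-sided at 0.05.

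**1. The plan's own figure.** For two proportions, n per arm = [1.96·√(2·0.25·0.75) + 0.84·√(0.4·0.6 + 0.1·0.9)]² / 0.3², which rounds up to 32, or 38 with the continuity correction. The stated 40 per arm is close to this. At 53 and 27, continuity-corrected power is 79.9%. So 80 participants for 80% power reproduces, although 40 in each arm does not fit 2:1. That is a separate point, and 53 and 27 are used below.

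**2. Parameters and events.**
- Parameters: treatment 1 + site 5 + sex 1 + age 1 + MSSS 1 = 9.
- Events: 27 × 0.4 + 53 × 0.1 = 16.1, and 16.1 / 9 = 1.8 per parameter.
- With a 33% placebo risk, close to the thyroid figure in the Background: 27 × 0.33 + 53 × 0.1 = 14.2, and 14.2 / 9 = 1.6.

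**3. Effect of the overload.** Simulation of 1,500 trials per scenario, with sites filled at random, follow-up of 2 to 4 years, and covariates that have no true effect. The true hazard ratio is ln(0.9) / ln(0.6) = 0.206.

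| Scenario | Quantity | Treatment only | 9 parameters |
|---|---|---|---|
| 40% vs 10% | Median HR | 0.20 | 0.17 |
| 40% vs 10% | Power, Wald | 86.1% | 83.5% |
| 40% vs 10% | Power, likelihood ratio | 86.5% | 84.5% |
| 40% vs 10% | Power, score | 88.5% | 85.2% |
| 20% vs 20% (about 16 events) | Type I error, likelihood ratio | 4.9% | 8.1% |
| 20% vs 20% | Type I error, score | 4.4% | 7.5% |
| 20% vs 20% | Type I error, Wald | 2.8% | 5.8% |
| 40% vs 40% (about 32 events) | Type I error, likelihood ratio | 5.0% | 6.2% |

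Because the covariates have no effect in these data, the shift in the hazard ratio is small-sample bias and not a change of estimand. Further simulations, one of them with unequal sites, gave a median adjusted hazard ratio of 0.16 to 0.17 and a likelihood-ratio type I error of 7.2% to 7.3%. At 40% vs 10%, between 36% and 41% of trials had at least one site with no events, so that site's coefficient had no finite estimate.

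**4. No events on rituximab.** P(0 of 53) = (1 − p)^53.

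| True rituximab risk | P(no events) |
|---|---|
| 10% | 0.4% |
| 5% | 6.6% |
| 3% | 20% |
| 2% | 34% |
| 1% | 59% |

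With a 40% placebo risk and no rituximab events, the 9-parameter Wald test rejected in 0% of trials, and the likelihood-ratio and score tests each in 99.9%. Such data are not ambiguous: Fisher's exact test of 0/53 against 11/27 gives p = 1.2 × 10⁻⁶. Simulated Wald power was 65% at a true 2% risk and 40% at 1%. That is nearly the chance of at least one rituximab event, 1 − 0.34 = 66% and 1 − 0.59 = 41%.

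**5. The alternative.** A site-stratified log-rank test was simulated with assumed site sizes 20/18/14/12/10/6 and 3-year follow-up. Type I error was 4.4% to 4.8%. Power was 87% to 88% at a 10% rituximab risk, 97% at 5%, and over 99% at 2%, 1% and 0%.

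**The case against.** A reader might infer that the rule cannot declare success if rituximab works completely, or that the better it works the less likely success becomes. The protocol does not support either reading. It names no Wald test, and the likelihood-ratio and score tests from the same model reject almost always when rituximab has no events. Even Wald power rises at first: one simulation gave 86% at a 10% rituximab risk and 93% at 5%, and it fell (to 75%) only by about 3%. At the design rate an empty arm is very unlikely.

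Three further points stand. Choosing a test statistic is commonly left to the analysis plan, which is not at hand, so its absence alone would be no fault. Sites without events do not break the treatment estimate: Wald power in trials with such a site was 84%, against 86% overall. And nine parameters assumes five site indicators; the protocol's wording would also allow site as a stratum, leaving four coefficients, or 16.1 / 4 = 4.0 events each.

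It is also fair to say that no single test shows both harms in full. Wald fails near zero events but has a two-sided type I error of only 5.8%, while likelihood ratio survives zero events but runs at 7% to 8%. However, the success rule is directional. In the null with about 16 events, the 9-parameter Wald and likelihood-ratio tests each favoured rituximab in 4.3% of trials, against a nominal 2.5%. The objection lowers the severity but does not make the model a good choice.

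**Conclusion.** The point holds at moderate severity. The covariates that the protocol fixes are too many for about 16 events. The consequences are a median hazard ratio of about 0.16-0.17 where 0.20-0.21 is right, and a likelihood-ratio type I error of about 7-8% with about 16 events under the null. With 40% in both arms, about 32 events, the error is milder at 6.2%. Power at the design rates remains above 80%, so this is not a loss of power.

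The success rule leaves the test open. The default Wald result would be unusable in an outcome that the objective names. That is improbable at a 10% risk (0.4%) but not if the effect is near-complete (34% at a true 2% risk). The 2% and 1% risks are illustrations, not design values.

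These sizes rest on site as five indicators, linear age and MSSS, constant hazards and no dropout. Separately, the protocol contradicts itself on whether age is a stratification factor.

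**What to change.** - Make the primary p-value a two-sided log-rank test stratified by site. Stata, the named software, does this with `sts test` and its strata option.
- Report the hazard ratio from a Cox model with site as a stratum and treatment, sex and age as covariates. Specify in advance a profile-likelihood or Firth-penalised estimate and interval for the case that an arm has no events.
- Reword the success rule to refer to the log-rank test, with the direction favouring rituximab.
- Move the model that also adjusts for MSSS to a sensitivity analysis.
- State one list of stratification factors in both Recruitment/Selection and Data Analysis.

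The cost is analysis wording only; design, sample size and data collection are unchanged. MSSS adjustment is no longer primary, the primary test itself does not adjust for sex or age, and the penalised hazard ratio may need a user-written routine.

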### b. Hypotheses

- *The following hypotheses will be tested:*
  - *1) Consecutive administration of alemtuzumab and rituximab is associated with a lower risk of autoimmune adverse events than when alemtuzumab is administered with placebo.*
  - *2) Consecutive administration of alemtuzumab and rituximab is associated with similar efficacy in MS disease control when compared to the administration of alemtuzumab with placebo.*
  - *3) Consecutive administration of alemtuzumab and rituximab is safe – adverse events will be no more common than when alemtuzumab is administered with placebo.*
  - *4) The early re-emergence of B-cells following alemtuzumab therapy is suppressed by the administration of rituximab when compared to placebo.*

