## **f. Risk Mitigation Procedures**

- *Treatment with alemtuzumab is associated with a risk (6-8%) of reactivation of HSV2 infection during the first month and a much lower level risk of listeria meningitis over the same time period. As is our usual practice all participants will receive valaciclovir 500 mg once daily for 30 days and Bactrim DS 960mg three times per week for 4 weeks commencing on the first day of therapy.*
- *In view of the potential additive risk of rituximab and alemtuzumab causing an increased risk of infection all participants will be advised to report any symptoms of fever, headache, neck stiffness, photophobia, shortness of breath, cough, abdominal pain or skin lesions to site investigators immediately.*
- *In view of the known risk of autoimmune adverse events with alemtuzumab (e.g. 30% risk of autoimmune thyroid disease) all participants will be monitored with monthly blood and urine tests through the Bloodwatch program. This is PBS mandated online monitoring program for all pwMS undergoing therapy with alemtuzumab which is sponsored by the manufacturer. This is standard of care for this therapy and includes monthly urine tests for red cells and protein, monthly blood tests for full blood count, urea and electrolytes and 3-monthly blood tests for TSH levels.*
- *Regular lymphocyte subset counts will be monitored and rituximab administration will be delayed if B-cell counts do not exceed 30% of pre-treatment levels.*

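### Infections are compared only by frequencies and chi-squared; if infections overall are common, adding a pooled infection rate ratio with a confidence interval would use the repeat episodes and be more informative

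*Protocol*

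**What the plan says.** The protocol's section on outcome measures lists "Other adverse events, in particular infections" as a secondary outcome. The section on risk mitigation explains why: "In view of the potential additive risk of rituximab and alemtuzumab causing an increased risk of infection", participants are told to report symptoms of infection at once. Hypothesis 3 states that "adverse events will be no more common than when alemtuzumab is administered with placebo".

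The section on data analysis gives one method for all of these. Other adverse events, by MedDRA term, "will be compared using frequencies and chi-squared statistics". It names no rate, person-time or recurrent-event method for them. It concedes that power for other adverse events and MS outcomes is probably insufficient, and adds that "these will be looked at carefully to ensure that these outcomes are similar in the two groups". For the primary outcome the same section chooses a Cox model, partly "Because the duration of follow up will not be uniform for all participants".

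On follow-up, the text under Figure 1 says: "Follow up will be for a minimum of 2 years and a maximum of 4 years". The study procedures place closeout at week 155 or earlier, and Table 3 ends at week 154. On dosing, the text under Figure 1 says: "Rituximab/placebo administered at Weeks 10 and 30 in each of Years 1 and 2".

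**The concern.** Infections differ from the primary outcome in that one person can have many. If frequencies means participants with at least one event, a person with one infection and a person with six count the same. When infections are common, most participants in both arms have at least one, and the two proportions approach a ceiling even if the underlying rates differ widely.

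The question asked of the data is also not one that a p-value answers. Hypothesis 3 and the stated wish to see that outcomes are similar call for an upper limit on the excess. A non-significant chi-squared test in 80 people gives none; a rate ratio with a confidence interval does.

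**Working it through.** **Inputs from the protocol.** 80 participants randomised 2:1, so about 53 rituximab and 27 placebo; follow-up of 2 to 4 years; study drug at weeks 10 and 30 after each alemtuzumab course (weeks 10, 30, 62 and 82 in Table 3). The protocol states no figure for infections overall, so there is none to reproduce. Its one infection figure, a 6–8% risk of HSV2 reactivation, concerns the first month, before the first study dose.

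**Assumptions.** Placebo rate λ of 0.25, 0.5, 1 or 2 infections per person-year; between-person gamma variance v of 0.5 or 1.0; follow-up T uniform on 2 to 4 years; rate doubled on rituximab only from week 10 to year 2; two-sided 5% level.

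**Size of the effect.** The window lasts 2 − 10/52 = 1.81 years. With mean follow-up of 3 years, the ratio over the whole of follow-up is 1 + 1.81/3 = 1.60.

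**Hand check at λ = 1, v = 0.5.**
- Rate ratio: the variance of the log rate per arm is about [1/(mean count) + v·E(m²)/(E m)²]/n, where m is a participant's expected count. Placebo: (1/3 + 0.5 × 1.037)/27 = 0.0316. Rituximab, mean count 4.81: (0.208 + 0.5 × 1.014)/53 = 0.0135. SE = √0.0451 = 0.212. Power ≈ Φ(ln 1.60/0.212 − 1.99) = Φ(0.23) = 59%.
- Chi-squared: 91% versus 83% have any infection. Pooled proportion 0.885, null SE 0.075, alternative SE 0.082. Power ≈ Φ((0.08 − 1.96 × 0.075)/0.082) = Φ(−0.83) ≈ 20%.

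**Simulation** (at least 20,000 trials per setting): Pearson chi-squared on any infection, against a log rate ratio with robust variance, an n/(n−1) correction per arm, and t with 78 df. Power, chi-squared versus rate test:

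| λ per year | v = 0.5 | v = 1.0 |
|---|---|---|
| 0.25 | 24% vs 34% | 19% vs 28% |
| 0.5 | 25% vs 49% | 17% vs 37% |
| 1 | 18% vs 61% | 15% vs 43% |
| 2 | 14% vs 70% | 11% vs 47% |

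The rate test rejects 5.1–5.8% of the time under no effect at v = 0.5.

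**Interval width if the rates are equal.** The 95% CI is the estimate times or divided by exp(1.99 × √{[1/(3λ) + 1.037v] × (1/53 + 1/27)}). At λ = 1, v = 0.5 this is exp(1.99 × √(0.852 × 0.0559)) = 1.54. Simulated factors are 1.89, 1.65, 1.53 and 1.46 for v = 0.5, and run from 2.03 to 1.64 for v = 1.0.

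**Where the gain ends** (v = 0.5, same window).
- Rate ratio 1.5 in place of 2: 12% vs 13%, 11% vs 18%, 10% vs 25%, 9% vs 29% across the four rates.
- λ = 0.1: 16% vs 17%. λ = 0.05: 10% vs 5%. λ = 0.02: 5% vs 0.2%.
- Half of all episodes unrecorded in both arms, doubled rate: 18% vs 20%, 24% vs 33%, 24% vs 48%, 18% vs 61%.

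**Recurrence or unequal follow-up?** With the rate doubled throughout and follow-up of 2 to 4 years, power is 41% vs 65%, 41% vs 83%, 28% vs 91%, 21% vs 96%. With nearly equal follow-up (2.5 to 2.98 years) it is 42% vs 63%, 42% vs 82%, 31% vs 92%, 22% vs 96%. The gap is the same, so recurrence produces it.

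**The case against.** The strongest reply is that the protocol contains no error here. Exposure-adjusted rates, episode rules and exact intervals often belong in an SAP, which is not at hand, and the bullet does not exclude them. That stands as a limit on severity. Even so, the protocol fixes a method for its one singled-out safety outcome, and a better addition is concrete and cheap.

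Further points that stand:
- The protocol does not define frequencies; participants with at least one event is the usual reading, not a stated one.
- The protocol compares by MedDRA term and does not mention pooling. Both simulated analyses pool all infections, so the table compares two ways of analysing pooled data, not the literal plan with the fix.
- Materiality rests on an assumed rate, variance and effect.
- Pooled counts may be driven by minor infections, while the gravest concerns, such as listeria meningitis, are rare events for which the rate test does not help.
- Equal under-recording in both arms assumes that blinding holds. Dosing depends on B-cell counts, which could reveal allocation to anyone who sees them.

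A reader might infer that unequal follow-up makes the planned test biased or invalid. The documents do not support this. Randomisation balances follow-up between arms in expectation, the visit schedule ends near week 155, and nearly equal follow-up leaves the comparison unchanged.

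**Conclusion.** The point holds as a minor, inexpensive improvement to a secondary safety analysis. On the usual reading, the stated method discards repeat infections and gives no limit on the excess that the data exclude. Under the assumptions above (pooled infections at about 0.25 per person-year or more, v of 0.5 to 1.0, doubled rate from week 10 to year 2), power rises from about 11–24% to 28–70%, and the CI factor is about 1.5 to 2.0. Below about 0.1 per year there is little or no gain, and at 0.05 per year or less the rate test is the weaker of the two.

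A reader might also infer that the change would give the trial adequate power to detect harm. It would not: at a rate ratio of 1.5 in the same window, power stays below about 30% with either method. The benefit there is an honest interval.

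**What to change.** Keep the numbers and percentages of participants by MedDRA term as planned. Add to the adverse-event bullet in the data analysis section:

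> For all infections combined, events per person-year will be given by arm, with a rate ratio and 95% CI from a Poisson model with log follow-up time as offset and small-sample-corrected robust standard errors. A new episode is counted only after a symptom-free gap (for example 14 days) fixed before unblinding. For serious infections and sparse terms, participants with at least one event will be given by arm, with an exact or mid-p 95% CI for the difference. Chi-squared will not be applied to event counts.

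One model should be named. The small-sample correction matters: in a separate check, a robust Poisson test using a normal reference rejected up to about 9% of the time under no effect.

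The cost is a few sentences, slightly more analysis and an episode rule. Adverse events and intercurrent illness are already reviewed every 6 months and at closeout, and follow-up time is known. The main weakness is reliance on recall of minor infections between those visits, some of which may be held by telehealth. If under-recording is equal in the two arms, it costs precision and does not bias the ratio.
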